#### 4.6 Description of Diets

Table 4 displays the nutrient targets of the three intervention diets at the 2100 kcal level. After randomization, participants are fed three diets, each of which is low in saturated fat **and cholesterol**. One diet, termed CARB, is based on the DASH diet; the CARB diet emphasizes carbohydrates (58% of kcal). Another diet, termed PROTEIN, emphasizes protein (25% of kcal), predominantly plant-based protein, while the third diet (UNSAT) emphasizes unsaturated fat (21% of kcal), predominantly monounsaturated fat. The three diets have a similar micronutrient profile and provide a similar amount of sodium, 2,300 mg per day in the 2,100 kcal diet. This level corresponds to the upper limit of current US recommendations for preventing and treating hypertension.

For each diet, five calorie levels are prepared (1600, 2100, 2600, 3100 and 3600 kcal). The macronutrient profile is identical at each calorie level. Micronutrient and fiber levels are identical to those of the DASH diet and are also identical across diets at the same calorie level (e.g. 5,700 mg of potassium in the 3,100 kcal level of each diet). The micronutrient levels are based on a Linear Index Model that indexes micronutrient levels to energy levels (Lin, 1999). This model is based on actual population consumption data and thus provides a realistic range of micronutrient intakes at lower and higher calorie levels, rather than a fixed ratio applied to all calorie levels (e.g. 4,700 mg of K per 2,100 kcal, or 2,238 mg of K per 1,000 kcal).

The CARB diet is a high carbohydrate diet (58% of kcal) similar to the DASH diet (55% of kcal from carbohydrate) that effectively lowered BP and reduced LDL-C without a change in triglycerides despite its relatively high carbohydrate content. This type of diet is currently recommended for the prevention and

treatment of hypertension (JNC VI, 1997). The DASH diet emphasizes fruits, vegetables and low-fat dairy products; includes whole grains, poultry, fish, and nuts; and is reduced in fats, red meats, sweets, and sugarcontaining beverages (Karanja, 1999). To establish a contrast in protein between the CARB and PROTEIN diets, we reduced the protein content of the DASH diet from 18% kcal to 15% kcal and increased the carbohydrate from 55 to 58% kcal. Otherwise, the CARB diet is similar to the DASH diet. Note that 15% kcal from PROTEIN is close to national estimates of average protein intake.

The PROTEIN diet provides 25% kcal from protein. While the protein sources are varied and include meat, dairy and plant sources, most of the increase in protein from the CARB diet (with 15% kcal from protein) to the PROTEIN diet (with 25% kcal from protein) comes from plants. The PROTEIN diet includes some soy products. However, soy products are not emphasized because of the potential for confounding from isoflavones that are present in variable amounts in certain preparations. Unfortunately, current nutritional databases are insufficient to estimate the soy content of foods. Hence, there are no specific quantifiable guidelines for the soy content of this diet or the other study diets.

The UNSAT diet is rich in unsaturated fat, predominantly monounsaturated fat. Accordingly, the distribution of monounsaturated, saturated, and polyunsaturated fats differs from the CARB and PROTEIN diets. This diet uses nuts, seeds, and oils such as olive, canola, and safflower oil to meet its target fat distributions. Specially formulated fat products are not used.

Table 4: Nutrient target levels of the study diets , 2100 kcal level				
	CARB	PROTEIN	UNSAT	
Carbohydrate (% kcal)	58	48	48	
Fat (% kcal)	27	27	37	
Saturated	6	6	6	
Monounsaturated	13	13	21	
Polyunsaturated	8	8	10	
Protein (% kcal)	15	25	15	
Meat	5.5	9.0	5.5	
Dairy	4.0	4.0	4.0	
Plant	5.5	12.0	5.5	
Cholesterol (mg/day)	150	150	150	
Fiber (g/day)	> 30	> 30	> 30	
Sodium (mg/day)	2300	2300	2300	
Potassium (mg/day)	4700	4700	4700	
Magnesium (mg/day)	500	500	500	
Calcium (mg/day)	1200	1200	1200	

# Table 4: Nutrient target levels of the study diets , 2100 kcal level

# 4.7 Menu development, evaluation, and monitoring

During the planning phase, a seven day menu cycle is developed for each diet (CARB, UNSAT, PROTEIN). In brief, the planning process involves preparation of 8 - 9 full day menus for each diet at each of 5 calorie levels (1600, 2100, 2600, 3100 and 3600); each full day menu is designed to meet the nutrient targets as displayed in Table 4. The difference between the nutrient target and the corresponding estimate from the Food Processor® software (version 7.9) is assessed. For each of the 3 seven day menu cycles, acceptable variation is a difference of  $\pm 1\%$  kcal for total fat, saturated fat, monounsaturated fat, polyunsaturated fat, carbohydrate, total protein, and plant protein. Acceptable variation (the difference as a percent of the target) is  $\pm 5\%$  for sodium, potassium, and calcium;  $\pm 10\%$  for magnesium; and  $\pm 50$  mg/**day** for cholesterol. In addition to the full day menus, diet-specific unit foods are developed to meet caloric needs between the calorie levels. The nutrient distribution of the unit foods corresponds to nutrient targets of the diet.

After menus are developed, recipes are taste tested for acceptance. Also, chemical (nutrient) analyses of composited menus are performed. Cost and feasibility considerations preclude chemical analyses of the 270 full day menus (9 candidate menus for each of 3 diets, at 5 calorie levels, at 2 sites). For this reason, composite analyses of just the 2100 kcal level are performed; this level was the most commonly used calorie level in the DASH and DASH-Sodium trials. Chemical analyses will include measurement of protein, carbohydrate, total fat, saturated fat, polyunsaturated fat, monounsaturated fat, sodium, potassium, magnesium, calcium and fiber. The final selection of menus is based on taste test results and chemical analyses of composited menus, as well as food production and cost considerations.

During the trial, menu monitoring is also performed. Once during each year of feeding, a full week of menus from each diet at the 2100 kcal level will be collected for composite analysis. In addition, analyses of urinary electrolyte excretion are also performed.

#### 4.8 Food Production and Distribution

Once menus are formulated, all foods are identified and selected to promote consistency at both feeding sites. Specific national brands are selected, as well as purchasing specifications for meats and produce. Detailed food preparation procedures and standardized recipes are developed to ensure that participants receive the same diets at the two feeding centers. Food production is also conducted according to respective state or county public health guidelines and JCAHO regulations. Quality control procedures developed in the DASH trials are used to monitor food procurement, preparation, and distribution. Research kitchens are monitored for safety, sanitation and equipment accuracy.

The process of preparing foods is a labor intensive process. In this process, food service workers weigh, portion, and package individual food items for the three diets, according to the calorie levels of the participants being fed. The cooks prepare all cooked items (e.g. casseroles, meats); in the process, they measure raw product, cook the items following standard hygienic procedures, and store the individualized portions. Some portion-controlled packaged food items are used for production efficiency. A diet technician assembles the trays for on-site meals and the bags and coolers for distribution of off-site meals, by diet and calorie level. A second person independently rechecks the assembled foods to confirm the accuracy of food delivery.

The feeding protocol is identical to that used in the DASH and DASH-Sodium trials. All study food is provided to participants who are instructed to eat all their food and to consume no additional food other than approved selected beverages. They are allowed to consume up to 2 alcoholic beverages per day and 3 non-caloric caffeinated beverages per day. Participants are required to eat one meal (the main meal of the day) at the feeding center Monday through Friday. The remaining food for the day and weekend food are provided for consumption off-site. On any given feeding visit, participants are expected to complete a daily food diary and be weighed. The daily diary asks about study foods not eaten, non-study foods eaten, and beverages consumed over the past day.

A dietitian case manager meets participants on a daily basis, receives and reviews their progress, elicits general feedback, tracks weight, and adjusts calorie level, if needed. The participant then proceeds to the dining area to eat the on-site meal. A meal monitor checks the completed tray and provides the take-home meals. On each day of feeding, participants complete a daily diary, which elicits information about food and beverage consumption over the preceding day, including non-alcohol beverages consumed, alcohol beverages

consumed, unit foods eaten, study foods not eaten, non-study foods eaten, and vitamin/supplement consumed.

#### 4.9 Promotion of Adherence

Efforts to promote adherence begin at the earliest stages of the study. During screening and orientation, participants are repeatedly provided with information about key features of the study. At the third screening visit, they are provided a detailed list of foods provided in the diets. Individuals must be willing to eat each of these foods; otherwise, they are excluded. Key contacts with dietary staff include a group orientation session during screening and an in-person evaluation by a dietitian. The intent of these efforts is to identify and exclude, prior to run-in and certainly prior to randomization, participants who are unwilling or unable to comply with the feeding protocol.

Once run-in feeding starts, participants get a chance to experience the actual demands of the study. At this time, efforts to promote adherence center on making the foods palatable and convenient to their lifestyles; maintaining easy access to staff; providing daily, supportive contacts; and providing a variety of items and incentives (raffle tickets, movie coupons) that promote good rapport. Acceptance of the controlled feeding protocol is increased by allowing participants to consume up to 3 non-caloric caffeinated beverages and 2 alcoholic beverages per day, as well as an unlimited amount of water and artificially sweetened soft drinks.

During a case conference at the end of run-in, the study dietitian, the study coordinator and principal investigator review all participants to assess their progress, continued interest and overall commitment to the trial. After randomization, every effort is made to promote adherence. In many instances, these efforts are tailored to the specific needs of the participant (e.g. meals delivered to home or work).

#### 4.10 Sample size

Table 5 displays the minimum detectable, between-diet differences for primary, secondary and other outcome variables in the full cohort (n=160) and in subgroups (n=80 and 70) at powers of 80% and 90% (2sided alpha, p=0.05). The sample size of the trial (n=160) was selected because it provided adequate power to detect between-diet differences in our primary outcome variables that have public health significance, both overall and in subgroups. Specifically, the minimum detectable effect size for our primary outcomes, systolic BP and LDL-C, are < 3 mmHg and < 10 mg/dl, respectively, even in subgroups that comprise 40 % (n=64) of participants. For instance, Stamler (1989) has estimated that a population wide 3 mmHg reduction in systolic BP will lower coronary heart disease mortality by 5% and stroke mortality by 8%. Furthermore, the BP effect sizes are plausible based on extrapolations from the INTERSALT observational study (Stamler, 1996), i.e. a difference in total protein intake of 40 gm per day (a conservative estimate of the contrast in protein between CARB and PROTEIN) is associated with a 3.2 mmHg reduction in systolic BP and 2.6 mmHg reduction in diastolic BP. Likewise, the small trial by Ferrara (2000), which documented a 7 mmHg reduction in systolic BP and 6 mmHg reduction in diastolic BP from replacing saturated fat with olive oil, suggests that our trial is sufficiently powered to detect more modest BP reductions from UNSAT in our population with lower BP. If non-hypertensives comprise 70% of study participants, the minimum detectable between-diet difference in SBP and DBP at 80% power is 1.7 and 1.3 mmHg for non-hypertensives and 2.6 and 2.0 mmHg for hypertensives. Corresponding estimates at 90% power are 2.0 and 1.5 mmHg for nonhypertensives and 3.1 and 2.3 mmHg for hypertensives.

For lipids, the minimum detectable effect sizes represent approximately 3% to 6% changes from expected mean concentrations (e.g. 140 mg/dl for LDL-C, 50 mg/dl for HDL-C, and 150 mg/dl for TG). For VLDL-apoB, the differences represent a 13% change from the mean (e.g. 12 mg/dl) for the full cohort and 20% for the n=80 subgroup. For VLDL-CIII, the differences represent a 10% change from the mean (e.g. 5 mg/dl) for the full cohort and a15% change for the n=80 subgroup. For fasting glucose, the differences represent 3 to 6% changes from typical mean values, e.g. 80 mg/dl. For fasting insulin and the insulin resistance index (HOMA), the differences represent changes of 20% and 8% from expected mean values of 5 uU/ml for insulin and 1.2 for HOMA (Mathews, 1985).

For the primary and secondary outcome variables, the standard deviation (SD) of change from beginning to end of the intervention periods in control subjects on the DASH trial were used to compute sample size requirements. These SDs were 6.4 mmHg for systolic BP, 4.8 mmHg for diastolic BP, 23 mg/dl for LDL-C, 5.4 mg/dl for HDL-C, 35 mg/dl for triglycerides, 7.6 mg/dl for fasting glucose, and 4.0 uU/ml for fasting insulin. The SDs for BP are based on means from clusters of 5 days of measurements. Because the eligibility criteria of the Omni-Heart and DASH trials are similar and because our recruitment strategies are likewise similar, these SDs are the most applicable. Still, the BP measurement technique of this trial (oscillometric) differs from that of the previous DASH trials (auscultatory); however, even if the actual SDs are slightly higher than projected, projected power should remain high, especially given the anticipated effect sizes (discussed below).

For the VLDL measurements, apoB and apo CIII, SDs of change are 6.1mg/dl and 2.0 mg/dl, respectively. These are based on the differences between baseline and 1 year in a random sample of 100 patients in the control group of the CARE trial ([name], unpublished). However, variability would be expected to be greater in free-living patients over 1 year than in our trial participants who eat in a controlled setting for 6 weeks. Hence, the minimum detectable differences derived from these SDs, while quite small, are likely to be greater than those actually detectable in this trial. For the insulin resistance HOMA index, the reproducibility data of Mathews (1985) was used, i.e. a CV of 31% (mean 1.2, SD 0.37).

 Table 5: Minimum Detectable Differences for Primary, Secondary and Other Outcome Variables for the

 Full Cohort (N=160) and Subgroups (N=80 and 70) at Powers of 80% and 90% (2-sided Alpha, P=0.05)

	Full Coh	ort (n=160)	Subgroup (n=80/n=70)			
Primary Outcomes	80 % Power	90 % Power	80 % Power	90 % Power		
SBP (mmHg)	1.4	1.7	2.0/2.2	2.3/2.5		
LDL-C (mg/dl)	5.1	5.9	7.3/7.8	8.4/9.0		
Secondary Outcomes						
DBP (mmHg)	1.1	1.2	1.5/1.6	1.8/1.9		
HDL-C (mg/dl)	1.2	1.4	1.7/1.8	2.0/2.1		
TG (mg/dl)	7.9	9.0	11.1/11.9	12.8/13.8		
Other Outcomes						
VLDL-apoB (mg/dl)	1.4	1.6	1.9/2.1	2.2/2.4		
VLDL-apo CIII (mg/dl)	0.45	0.52	0.63/0.68	0.73/0.79		
Glucose (mg/dl)	1.7	2.0	2.4/2.6	2.8/3.0		
Insulin (uU/mI)	0.89	1.0	1.3/1.4	1.5/1.6		
Insulin resistance index (HOMA)	0.082	0.095	0.12/0.13	0.14/0.15		

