#### 4.4.2 Lipids, glucose and insulin

Traditional lipid fractions, glucose and insulin are measured at baseline and in weeks 4 and 6 of the 3 dietary periods from blood collected after an overnight (8-12 hour) fast and then stored at -70C. Apolipoproteins and Lp(a) will be measured in week 6; depending on sufficient resources, these variables will also be measured at baseline and/or in week 4. At the CLCS laboratory directed by [name], plasma total cholesterol and glycerol-blanked triglycerides are measured using enzymatic kits from Miles-Technicon and Roche on the Hitachi 917 analyzer. HDL-C is measured as above in the supernatant of plasma after the precipitation of apo B-containing lipoproteins with dextran sulfate (50,000 MW, Genzyme). Glucose is measured using the enzymatic hexokinase kit from Roche on the Hitachi 917. Insulin is measured using Microparticle Enzyme Immunoassay technology on the Abbott IMx analyzer. Consistency of measurement is evaluated by an in-house Quality Assurance program based on the standard Westgard rules for analytical run acceptance. Accuracy of measurement is verified by participation in the CDC Lipid Standardization Program, the CDC Cholesterol Reference Method Laboratory Network, the Pacific Biometrics, Inc., ALERT Program and the College of American Pathologists external proficiency program. Accuracy of cholesterol, HDL cholesterol and triglyceride measurements are also evaluated by a comparison of routine methods to reference methods or designated comparison methods in-house using patient specimens.

From the fasting glucose and insulin levels, the HOMA insulin resistance is calculated (fasting plasma insulin concentration in uU/ml x fasting plasma glucose concentration in  $mmol/l \div 22.5$ ). Quantification of insulin resistance using this model has been validated using a euglycemic hyperinsulinemic clamp, a hyperglycemic clamp, monocyte and erythrocyte insulin receptor status; the HOMA index also correlates well with the degree of obesity (Matthews 1985).

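### Table 5's detectable difference for HOMA (0.082) conflicts with the protocol's own insulin and glucose SDs and is too small by about a factor of 2

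*Protocol*

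**What the plan says.** Section 4.10 and Table 5 give minimum detectable between-diet differences "in the full cohort (n=160) and in subgroups (n=80 and 70"), "at powers of 80% and 90% (2sided alpha, p=0.05").

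For the BP, lipid, glucose and insulin rows, "the standard deviation (SD) of change from beginning to end of the intervention periods in control subjects on the DASH trial were used". The glucose SD is 7.6 mg/dl and the insulin SD 4.0 uU/ml. The two VLDL rows also use SDs of change, from the control group of another trial. HOMA alone rests on reproducibility data from a cited study, given as "a CV of 31% (mean 1.2, SD 0.37"). The section does not say whether this SD belongs to one measurement or to a difference between two.

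The Table 5 row "Insulin resistance index (HOMA") reads 0.082 and 0.095 for n=160 at 80% and 90% power, 0.12 and 0.14 for n=80, and 0.13 and 0.15 for n=70. The text adds that "the differences represent changes of 20% and 8% from expected mean values of 5 uU/ml for insulin and 1.2 for HOMA".

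Section 4.4.2 defines the index as insulin (uU/ml) times glucose (mmol/l) divided by 22.5. Section 4.11 makes the Aim 3 outcomes within-person differences between two diets, in the same way as for Aims 1 and 2.

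**The concern.** HOMA is a product of insulin and glucose. Over the range in question it should be about as variable, in relative terms, as its noisier factor, which is insulin. Yet the protocol puts the detectable change at 20% for insulin and 8% for HOMA, from the same blood samples, the same participants and the same test. Both cannot hold unless insulin and glucose changes offset each other to a degree that the stated SDs rule out.

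At stake is the stated sensitivity of Specific Aim 3. A reader who relies on Table 5 would believe the trial well placed to detect a HOMA change that, on the document's own inputs, it would detect with power well below 80%.

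**Working it through.** **Reproducing the plan's figure.** For a paired comparison, detectable difference = SD of the difference × (z for two-sided 0.05 + z for power) / √n. The z sum is 2.802 at 80% power and 3.242 at 90%.

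- 0.37 × 2.802 / √160 = 0.0819
- 0.37 × 3.242 / √160 = 0.0948

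These are the printed 0.082 and 0.095, so 0.37 was used unchanged as the SD of the between-diet difference. The same formula with the stated SDs of change reproduces the other rows to rounding (for example insulin 0.89 and glucose 1.7). The largest gap is triglycerides, 7.8 against 7.9.

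**Check 1: HOMA row against insulin row.** The inputs are mean glucose 80 mg/dl (section 4.10), converted to 4.44 mmol/l by an assumed 18 mg/dl per mmol/l, and the formula in section 4.4.2. With glucose held at that level, a HOMA change of 0.082 is an insulin change of 0.082 × 22.5 / 4.44 = 0.42 uU/ml. Table 5 gives 0.89 uU/ml as the smallest insulin change detectable at the same n and power, so 0.42 is under half of it.

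**Check 2: relative SDs.** Insulin: 4.0/5 = 80%. Glucose: 7.6/80 = 9.5%. HOMA as entered: 0.37/1.2 = 31%. To first order, the relative SD of a change in the product is √(0.80² + 0.095² + 2r × 0.80 × 0.095), where r is the correlation of insulin and glucose changes. The protocol does not give r, so the whole range is shown:

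- r = −1: 70.5%
- r = 0: 80.6%
- r = +1: 89.5%

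No correlation gives 31%.

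**Check 3: size of the understatement.** Two scalings from insulin alone are possible, because the stated means disagree: 5 × 4.44 / 22.5 = 0.99, not 1.2.

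- At glucose 80 mg/dl: SD = 4.0 × 4.44 / 22.5 = 0.79. This term does not involve mean insulin.
- Applying 80% to the stated HOMA mean: SD = 0.80 × 1.2 = 0.96.

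| n | Power | Printed | SD 0.79 | SD 0.96 |
|---|---|---|---|---|
| 160 | 80% | 0.082 | 0.175 | 0.213 |
| 160 | 90% | 0.095 | 0.202 | 0.246 |
| 80 | 80% | 0.12 | 0.25 | 0.30 |
| 80 | 90% | 0.14 | 0.29 | 0.35 |
| 70 | 80% | 0.13 | 0.26 | 0.32 |
| 70 | 90% | 0.15 | 0.31 | 0.37 |

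At n=160 and 80% power the ratios to the printed figure are 0.175/0.082 = 2.1 and 0.213/0.082 = 2.6. Adding glucose over all correlations, with either mean, gives 0.154 to 0.238, or factors of 1.9 to 2.9. Power to detect 0.082 is about 26% with SD 0.79, and 16% to 32% over the full range.

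**Check 4: the percentages in the text.** The printed 20% and 8% come from the 90% power column: 1.0/5 = 20% and 0.095/1.2 = 7.9%. Like for like, the HOMA figure is 0.202/1.2 = 17% to 0.246/1.2 = 21%. The lower value divides a result built at a mean of 0.99 by 1.2. With one mean used throughout it is 0.202/0.99 = 20%, or 0.246/1.2 = 20.5%, in line with insulin.

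**The case against.** The best defence is that the arithmetic is correct and the input is openly disclosed, with its source. HOMA belongs to Other Specific Aims, and Aim 3 only assesses it, without a directional hypothesis. Section 4.10 says that n=160 was chosen for the primary outcomes. Section 4.11 promises 95% confidence intervals with all estimates, and these will show the precision achieved whatever SD was planned. All of this stands, and it limits the severity. It does not reconcile two rows of one table.

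Section 4.10 contains two cautions about its SDs, but neither covers this. The remark that actual SDs may be slightly higher concerns the BP technique. The remark that detectable differences are probably overstated concerns the VLDL rows.

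Three stronger readings are tempting and are not supported:

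- **That 0.37 is the SD of a single measurement**, so that the paired SD is 0.37 × √2 = 0.52 and the detectable difference 0.116. The words reproducibility and CV suggest this, but the protocol does not say it and the source is not at hand. The factor of 1.4 is therefore conditional. It is also not the lower end of a range with the factors above, since 0.52 would still be too small beside the insulin SD.
- **That the trial cannot detect an 8% change in HOMA.** The SD that the trial will observe is unknown. What can be said is that the stated inputs do not support the claim.
- **That a null HOMA result would be misread.** The planned confidence intervals guard against that.

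**Conclusion.** The HOMA row is wrong as written, because it contradicts the insulin and glucose inputs in the same section. It is too small by about a factor of 2: 2.1 to 2.6 by scaling from insulin, and 1.9 to 2.9 over all correlations.

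The conclusion rests on the protocol's stated SDs and means, on its HOMA formula, on a first-order approximation for the product, and on the glucose unit conversion. It does not depend on what 0.37 measures.

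The severity is minor. A reader might infer that the trial is too small, but the documents do not support that: sample size, primary and secondary outcomes and tests are unaffected.

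**What to change.** Recompute the HOMA row of Table 5, including the n=80 and n=70 cells, from an SD of change. The best source is the change in HOMA among the DASH control participants, who already supply the insulin and glucose SDs.

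If that is not available, derive the row from the stated insulin and glucose SDs, and give the assumption and range:

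- n=160: about 0.175 to 0.21 at 80% power (0.15 to 0.24 over all correlations) and 0.20 to 0.25 at 90%
- n=80: about 0.25 to 0.30 at 80% power and 0.29 to 0.35 at 90%
- n=70: about 0.26 to 0.32 at 80% power and 0.31 to 0.37 at 90%

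In the text of section 4.10, replace 8% with the matching 90% power figure, about 17% to 21%. Reconcile the expected means, since 5 uU/ml and 80 mg/dl give a HOMA of 0.99 rather than 1.2; with one mean used throughout, the figure settles near 20%.

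The cost is one table row and one or two sentences, and a less favourable figure for an outcome outside the primary and secondary set. Nothing in the design or conduct changes.
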